3.1.1 Dose Escalation

Subjects with platinum-resistant ovarian, primary peritoneal, or fallopian tube cancer will be enrolled in dose escalation cohorts to receive either SL-172154 with PLD or SL-172154 with MIRV. For Regimen (SL-172154 + MIRV), subjects must have a tumor that is positive for FR α expression (PS2+ $\geq 25\%$) as defined by the Ventana FOLR1 Assay. Subjects can be enrolled to only 1 of the combination regimens in this study.

SL-172154 Administered with PLD

SL-172154 (3.0 mg/kg starting dose) will be administered by intravenous (IV) infusion on Days 8 and 15 of each 28-day cycle. PLD (40 mg/m², IV) will be administered on Day 1 of each 28-day cycle.

The planned dose escalation of SL-172154 is outlined in Table 1; additional doses and/or schedules may be explored based on emerging safety, PK and PD data.

Subjects will be enrolled in cohorts of approximately 3 subjects into sequential dose levels of SL-172154 administered with PLD and evaluated for DLT during the 28-day DLT evaluation period. Treatment will be administered in 28-day cycles until at least one of the study treatment discontinuation criteria is met. The safety as well as available PK, PD, and efficacy data from these subjects will inform the dose of SL-172154 selected to be further evaluated in Dose Expansion.

Table 1 SL-172154 Dose Escalation Plan When Administered with PLD

Dose Level ^a	SL-172154 Dose ^b [D8 and 15 in each 28d cycle]	SL-172154 Infusion ^c	Pegylated liposomal doxorubicin (PLD)
-1 ^d	1.0 mg/kg	60 min ± 10 min	PLD (40 mg/m ²) IV administered on Day 1 of each 28-day cycle
1 (Starting Dose)	3.0 mg/kg	120 min ± 15 min	Administer first dose on study (C1D1) as 1 mg/min IV infusion; after Cycle 1, if tolerated, PLD can be delivered as a 1-hour infusion
2	6 mg/kg	120 min ± 15 min	

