
a. Doses explored in SL03-OHD-105 will not exceed the highest dose determined to be safe and tolerable in the ongoing monotherapy dose escalation study SL03-OHD-101.
 
b. The actual body weight in kilograms (kg) will be used for SL-172154 dose calculation in all subjects whose body weight is ≤100 kg. For subjects with body weight >100 kg, the dose to be administered should be the same as that calculated for a subject weighing 100 kg.
 
c. Infusion time may change based on final drug volume needed for administration, safety and tolerability of the infusion for the subject and/or observed safety findings during the study. Please refer to the Study Pharmacy Manual (SPM) for details.
 
d. SL-172154 dose level -1 at 1.0 mg/kg will be evaluated if 3.0 mg/kg is not safe per mTPI-2.
			

SL-172154 Administered with MIRV

SL-172154 (3.0 mg/kg starting dose) will be administered by IV infusion on Day 8 and Day 15 of 21-day cycles. MIRV (6 mg/kg AIBW, IV) will be administered on Day 1 of each 21-day cycle.

The planned dose escalation of SL-172154 is outlined in Table 2; additional doses and/or schedules or intermediate doses may be explored based on emerging safety, PK, and PD data.

Subjects will be enrolled in cohorts of approximately 3 subjects into sequential dose levels of SL-172154 administered with MIRV and evaluated for DLT during the 21-day DLT evaluation period. Treatment will be administered in 21-day cycles until at least one of the study treatment discontinuation criteria is met.

The safety as well as available PK, PD, and efficacy data from these subjects will inform the dose of SL-172154 selected to be further evaluated in Dose Expansion.

Table 2 SL-172154 Dose Escalation Plan When Administered with MIRV

Dose Level ^a	SL-172154 Dose ^b [D8 and D15 in each 21d cycle]	SL-172154 Infusion ^c	Mirvetuximab soravtansine (MIRV) ^e
-1 ^d	1.0 mg/kg	60 min \pm 10 min	6 mg/kg AIBW, IV administered on Day 1 of each 21-day cycle
1 (Starting dose)	3.0 mg/kg	120 min \pm 15 min	Administer 1st dose on study (C1D1) at rate of 1 mg/min; after 30 min increase rate to 3 mg/min if well tolerated. If well-tolerated after 30 min at 3 mg/min, infusion rate may be increased to 5 mg/min. Subsequent infusions should be delivered at the tolerated rate.
2	6 mg/kg	120 min \pm 15 min	

AIBW = adjusted ideal body weight

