3.4 Study Treatment Discontinuation Criteria

A subject will receive the assigned study treatment (e.g., SL-172154 and PLD or SL-172154 and MIRV) until any of the following events occur during the study:

- Documented disease progression (radiological or clinical)
- A subject suffers an AE that, in the judgement of the investigator, Sponsor, or medical monitor, presents an unacceptable risk to the subject
- General or specific changes in the subject's condition (e.g., a significant intercurrent illness or complication) that, in the judgement of the investigator, are unacceptable for further administration of study treatment
- Subject decides to discontinue further study treatment
- Occurrence of pregnancy
- Significant non-compliance with protocol requirements
- Death
- Termination of the study by Sponsor

If one agent in the assigned regimen is permanently discontinued for any reason, at the investigator's discretion, the subject may continue to receive the other agent in the assigned regimen as monotherapy until meeting one of study treatment discontinuation criteria.

In the event of permanent discontinuation of all study treatment, subjects should be strongly encouraged to complete all scheduled assessments at the Post Treatment visit and the Survival Follow-up contacts.

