4. ANALYSIS POPULATIONS

The populations defined for analysis will include the following:

Population	Description
Screened	All subjects who have signed the main study Informed consent form (ICF).
Screen Failures	All subjects who have signed the main study ICF but have not received any study treatment.
All Treated	All subjects who receive at least one dose of study drug (SL-172154, PLD, or MIRV). Safety data will be evaluated based on this population.
DLT Evaluatable	All subjects enrolled in the dose escalation cohorts who receive at least 50% of the scheduled doses of SL-172154 and 1 dose of PLD or MIRV and complete the safety follow-up through the DLT evaluation period or experience any DLT during the DLT evaluation period. DLT evaluable subjects will be used to guide dose escalation and to determine the MTD or MAD.
Response Evaluatable	Subjects in the All Treated Population who have either had at least one post-baseline disease assessment or who have discontinued study treatment due to disease progression or death before any post-baseline disease assessment.
SL-172154 Pharmacokinetic	Subjects in All Treated Population who have at least one post SL-172154 dose PK sample obtained and analyzed.
SL-172154 Immunogenicity	Subjects in the All Treated Population who have at least one post SL-172154 dose immunogenicity measurement.
MIRV Pharmacokinetic	Subjects in All Treated Population who have at least one post MIRV dose PK sample obtained and analyzed.
MIRV Immunogenicity	Subjects in the All Treated Population who have at least one post MIRV dose immunogenicity measurement.
MIRV FRa Pre-screened	All subjects in MIRV regimen who have signed the pre-screen informed consent form for FRa test.

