Continuous variables will be summarized with means, standard deviations, medians, minimums, and maximums. The precision of the original measurements will be maintained in summaries and listings, when possible. Generally, means and medians will be presented to one more decimal place than the raw data, and the standard deviations will be presented to two more decimal places than the raw data.

Categorical variables will be summarized by counts and by percentages of subjects in the corresponding categories. Percentages are routinely based on the total number of the specified population N if not specified otherwise. For frequency counts, categories whose counts are zero will be displayed for the sake of completeness. For example, if none of the subjects discontinue

due to “lost to follow-up”, this reason will be included in the table with a count of 0. Categories with zero counts will not have zero percentages displayed.

All confidence intervals (CIs) will be constructed at the 95% confidence level, unless specified otherwise.

All analyses and tabulations will be performed using SAS® v9.4 or above.

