8. SAFETY ANALYSES

Unless specified otherwise, all safety data summaries will be presented by dose levels for all subjects in the All Treated population for each treatment regimen. Select safety summaries will be provided for DLT evaluable populations.

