- **PT rows:** each subject is counted once within each unique PT at the maximum grade. For example, if a subject has two headaches, the subject is counted only once under the PT “Headache”. Subjects experiencing the same PT several times with different grades will only be counted once at the maximum grade.
- **SOC rows:** each subject is counted only once at the maximum grade at each SOC level although they may have several different PT events within the same SOC.
- **Any event row:** each subject with at least one TEAE will be counted only once at the maximum grade no matter how many events they have.

All TEAEs and drug-related TEAEs will be summarized by MedDRA SOC, PT and maximum toxicity grade. The SOC and PT will be ordered by descending order of the subject incidence of SOC and PT within each SOC based on all subjects in the analysis population.

The following summary tables will be presented by MedDRA PT, in which the PT will be order by descending order of subject incidence of PT based on all subjects in the analysis population:

- Summary of all TEAEs
- Summary of DLTs
- Summary of serious TEAEs
- Summary of drug-related TEAEs (separate tables for SL-172154, PLD, and MIRV)
- Summary of drug-related serious TEAEs (separate tables for SL-172154, PLD, and MIRV)
- Summary of fatal TEAEs
- Summary of Grade 3 or 4 TEAEs

- Summary of drug-related Grade 3 or 4 TEAEs (separate tables for SL-172154, PLD, and MIRV)
- Summary of TEAEs leading to infusion interrupted, dose reduced, dose not given/delayed, and drug withdrawn (separate tables for SL-172154, PLD, and MIRV)

Additional summaries for SL-172154-related IRR (toxicity grade, seriousness, number of events, action taken) at event-level, at subject-level, and number of subjects with IRR at each dosing visit among the first two cycles and during all subsequent cycles combined will be provided. For the MIRV cohort, MIRV-related Grade 3 or 4 ocular toxicity TEAEs, with SOC='Eye disorders', will be listed and summarized.

Listings of all AEs, drug-related AEs, DLTs, Grade 3 or 4 AEs, fatal AEs, and SAEs will be provided. Separate listings will be provided for AEs leading to infusion interruption, dose reduction, dose not given/delayed, and drug withdrawal with SL-172154, PLD, and MIRV, respectively. SL-172154-related IRR along with signs/symptoms, premedication and concomitant medication for IRR will also be listed. All AEs for the Screen Failures population will be presented in a listing as well.

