	14.3.1.14.2	Toxicity Grade 3 and Above Adverse Events by Preferred Term	All Treated	Yes
	14.3.1.15.1	SL-172154-Related Grade 3 or 4 Adverse Events by Preferred Term	All Treated	Yes
	14.3.1.15.2	PLD-Related Serious Grade 3 or 4 Events by Preferred Term	All Treated	Yes
	14.3.1.16.1	Adverse Events Leading to SL-172154 Infusion Interrupted by Preferred Term	All Treated	Yes

ICH Heading	Table Number	Table Description	Analysis Population	aCSR
	14.3.1.16.2	Adverse Events Leading to PLD Infusion Interrupted by Preferred Term	All Treated	Yes
	14.3.1.17.1	Adverse Events Leading to SL-172154 Dose Reduced by Preferred Term	All Treated	Yes
	14.3.1.17.2	Adverse Events Leading to PLD Dose Reduced by Preferred Term	All Treated	Yes
	14.3.1.18.1	Adverse Events Leading to SL-172154 Dose Not Given or Delayed by Preferred Term	All Treated	Yes
	14.3.1.18.2	Adverse Events Leading to PLD Dose Not Given or Delayed by Preferred Term	All Treated	Yes
	14.3.1.19.1	Adverse Events leading to SL-172154 Drug Withdrawn by Preferred Term	All Treated	Yes
	14.3.1.19.2	Adverse Events leading to PLD Drug Withdrawn by Preferred Term	All Treated	Yes
	14.3.1.20.1	Summary of SL-172154-Related Infusion Related Reaction at Subject Level	All Treated	No
	14.3.1.20.2	Summary of Symptoms of SL-172154-Related Infusion Related Reaction at Subject Level	All Treated	Yes
	14.3.1.20.3	Summary of Symptoms of SL-172154-Related Infusion Related Reaction at Event Level	All Treated	Yes
	14.3.1.21.1	Summary of SL-172154-Related Infusion Related Reaction at Event Level	All Treated	Yes
	14.3.1.22.1	Summary of SL-172154-Related Infusion Related Reaction by Dosing Visit	All Treated	No
	14.3.1.23	Deaths	All Treated	Yes
	14.3.1.24b	MIRV-Related Grade 3 or 4 Ocular Toxicity Treatment-Emergent Adverse Events by Preferred Term	All Treated	Yes
14.3.5		Laboratory		
	14.3.5.1	Hematology – Maximum CTCAE Grade Shift from Baseline	All Treated	No
	14.3.5.2	Chemistry – Maximum CTCAE Grade Shift from Baseline	All Treated	No
	14.3.5.2.2	Liver Function Tests – Maximum CTCAE Grade Shift from Baseline	All Treated	Yes
	14.3.5.3	Coagulation – Maximum CTCAE Grade Shift from Baseline	All Treated	No
	14.3.5.4	Laboratory Tests without CTCAE - Maximum Shift from Baseline with Respect to Normal Range	All Treated	No
	14.3.5.5	Post-Baseline Potential Serious Hepatotoxicity	All Treated	Yes
14.3.6		Other Safety Data		
	14.3.6.1	ECOG Performance Status – Maximum Shift from Baseline	All Treated	Yes
14.3.7		PK Data		

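### By-visit SL-172154 infusion reactions are set against All Treated rather than the subjects infused at that visit, so they can be understated and can appear to fall across the first four infusions through attrition alone

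*SAP*

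**What the plan says.** SAP 8.3 promises, for SL-172154-related IRR, the "number of subjects with IRR at each dosing visit among the first two cycles and during all subsequent cycles combined". The matching entry in SAP 13.1 is Table 14.3.1.22.1, "Summary of SL-172154-Related Infusion Related Reaction by Dosing Visit", with All Treated in the population column.

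Three general rules then apply:

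- SAP 8 states that, unless specified otherwise, "all safety data summaries will be presented by dose levels for all subjects in the All Treated population for each treatment regimen".
- SAP 4 admits a subject to All Treated after one dose of any of SL-172154, PLD or MIRV.
- SAP 5.2 sets the default base: "Percentages are routinely based on the total number of the specified population N if not specified otherwise".

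On timing, SAP 3.1.1 gives PLD and MIRV on Day 1. For the PLD regimen, "SL-172154 (3.0 mg/kg starting dose) will be administered by intravenous (IV) infusion on Days 8 and 15 of each 28-day cycle"; for the MIRV regimen, SL-172154 "will be administered by IV infusion on Day 8 and Day 15 of 21-day cycles". SAP 3.4 adds that if one agent is permanently stopped, "the subject may continue to receive the other agent in the assigned regimen as monotherapy". Protocol 3.7 treats an SL-172154 dose that is not given as skipped, without delaying the cycle. Protocol 3.7.1.1 requires permanent discontinuation of SL-172154 after certain IRRs.

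No SL-172154-exposed safety set and no number-infused-at-visit denominator is defined. SAP 4 does define SL-172154-specific PK and immunogenicity populations, each requiring a sample taken after an SL-172154 dose.

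**The concern.** A by-visit IRR table is read for one purpose: whether reactions become less frequent with repeat infusions. That needs the number at risk at each infusion. Under the SAP defaults, a subject who skipped the dose, had not yet received SL-172154 or had stopped it stays in the denominator and looks like someone infused without a reaction. Some of those subjects will have stopped because they reacted, so the missing exposure is linked to the outcome.

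IRR was the most frequent adverse event in the monotherapy study (Protocol 1.4.7), safety is a primary objective, and Protocol 3.4 bases the recommended dose on all the safety data taken together. A decline produced only by shrinking exposure could be read as tolerance developing.

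A lesser form of the same problem affects subject-level SL-172154-related AE, IRR and SL-172154-withdrawal tables, where the denominator includes anyone lost between Day 1 and Day 8.

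**Working it through.** **Inputs from the documents.** The dosing days, the All Treated definition, the default percentage base and the table assignment are as set out above. Regimen sizes at the selected dose are about 70 (MIRV) and about 20 (PLD), from SAP 3.1.2. The only IRR rate available is from the monotherapy study in Protocol 1.7.1: 17/26 = 65.4%, which reproduces. It serves only as an anchor.

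**Inputs not in the documents, so assumed.** Per-infusion IRR risk p = 30% (range 20% to 40%), constant over visits. Share of All Treated infused at C1D8, C1D15, C2D8 and C2D15 = 97%, 93%, 85%, 80%; as a second pattern, 67, 63, 58 and 53 of 70. Share with any infusion in later cycles s = 65% (range 50% to 70%). Subjects never given SL-172154: 0 to 10%.

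**Step 1, single-visit rows.** Displayed rate = p × (number infused / N).

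First pattern, p = 30%: 0.30 × 0.97 = 29.1%; 0.30 × 0.93 = 27.9%; 0.30 × 0.85 = 25.5%; 0.30 × 0.80 = 24.0%.

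Second pattern, N = 70:

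| True risk | C1D8 (67) | C1D15 (63) | C2D8 (58) | C2D15 (53) |
|---|---|---|---|---|
| 20% | 19.1% | 18.0% | 16.6% | 15.1% |
| 30% | 28.7% | 27.0% | 24.9% | 22.7% |
| 40% | 38.3% | 36.0% | 33.1% | 30.3% |

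Bare counts show the same thing. At 30% the expected numbers are 20.1, 18.9, 17.4 and 15.9. Divided by the number infused, every visit returns the true risk.

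**Step 2, pooled later-cycles row.** SL-172154 is given twice per cycle, so a subject has several chances to be counted. With m later infusions treated as independent, displayed rate = s × [1 − (1 − p)^m]. At s = 65% and p = 30%:

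- m = 1: 0.65 × 0.30 = 19.5%
- m = 2: 0.65 × (1 − 0.7²) = 0.65 × 0.51 = 33%
- m = 4: 0.65 × (1 − 0.7⁴) = 0.65 × 0.76 = 49%

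Over s = 50% to 70% the ranges are 15.0–21.0%, 25.5–35.7% and 38.0–53.2%. With two or more infusions the row can exceed the first-visit figure. Dividing by subjects with any later infusion does not solve this: it gives 51% (m = 2) or 76% (m = 4), a spurious rise at constant risk. Infusions with IRR divided by infusions given returns 30%.

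**Step 3, subject-level tables.** Displayed rate = 65.4% × (N − k)/N, where k subjects never received SL-172154. For N = 70 and k = 0, 4, 7: 65.4%, 61.7%, 58.9%. For N = 20 and k = 0, 1, 2: 65.4%, 62.1%, 58.9%.

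**The case against.** The strongest reply is that SAP 8.3 promises a number of subjects by visit, not a rate. Elsewhere in the same section it names counts and percentages when it wants both. The percentage follows only from a default in SAP 5.2 that yields to other specification, and the table shells are not among the documents. This stands as a limit on what can be asserted, but it does not rescue the table, because counts without the number infused mislead in the same direction.

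Second, All Treated is the protocol's own safety population (Protocol 9.2.1 and 9.2.4) and suits a study of a combination. That is right for combination-level AE tables. It is less apt for events attributed to one agent that starts a week later.

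Third, exposure can be recovered elsewhere: SAP 8.1.2 summarises SL-172154 doses and infusion outcomes, and every administration is listed. True, but the by-visit table does not then stand on its own.

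Fourth, the practical reach is limited. Dexamethasone premedication is already in the current protocol, escalation and MTD use the DLT-evaluable set, and Table 14.3.1.22.1 is marked as not produced for the abbreviated report. The first two points lower the stakes. The last matters only if the study ends early (SAP 13).

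**Conclusion.** The point holds for the by-visit IRR summary. Followed as written, the plan puts subjects who were not infused into the base, or gives counts with no base. Either can understate IRR and can show a decline over the four single-visit rows when risk is constant. Under the assumed exposure patterns and a 30% risk, the displayed figure drops by about 5 to 6 percentage points between C1D8 and C2D15. The exposure shares and per-infusion risks are all assumptions; the direction of the bias is not.

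A reader might infer two stronger conclusions that the documents do not support:

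- That attrition makes IRR appear to fall throughout repeat dosing. The pooled later-cycles row accumulates infusions and may well rise.
- That every SL-172154 rate is materially diluted. Subject-level dilution is confined to subjects lost between Day 1 and Day 8. The documents give no such number, so the effect is probably small and may be zero.

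**What to change.** In SAP 8.3 and the specification of Table 14.3.1.22.1:

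- For each single visit in Cycles 1 and 2, print the number of subjects infused with SL-172154 and use it as the denominator.
- For later cycles, report infusions with IRR divided by infusions given.
- For subject-level SL-172154-related AE, IRR and SL-172154-withdrawal tables, base percentages on subjects with at least one SL-172154 infusion.
- Keep All Treated for combination-level AE tables.

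A number-infused denominator removes the attrition artefact but not selection. Subjects still infused at later visits may be those who tolerated earlier doses, so the printed number should be read alongside the rate.

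The cost is SAP wording and minor programming, with no new data, since SAP 8.1.2 already uses the administration records. Some rates may become slightly less favourable.

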8.4 Clinical Laboratory Evaluation

The clinical laboratory evaluation includes the following:

- Hematology: hemoglobin, hematocrit, platelet count, red blood cell count, white blood cell count, neutrophils, lymphocytes, monocytes, eosinophils, basophils, and mean corpuscular volume
- Clinical chemistry: blood urea nitrogen, creatinine, glucose, sodium, potassium, calcium, magnesium, phosphorus, total protein, albumin, lactate dehydrogenase, bicarbonate (or CO₂), haptoglobin, ferritin and liver panel [alanine aminotransferase (ALT), aspartate aminotransferase (AST), total and direct bilirubin, and alkaline phosphatase].
- Coagulation: prothrombin time, international normalized ratio, activated partial thromboplastin time, fibrinogen, and D-dimer.
- Thyroid: thyroid stimulating hormone and free thyroxine 4.

The clinical laboratory grades will be reported using the CTCAE v5.0. Separate listings will be provided for hematology, clinical chemistry, coagulation and thyroid tests. For each listing, baseline value will be specified for each subject.

Clinical laboratory results (hematology, clinical chemistry, coagulation) will be summarized for worst case shift from baseline toxicity grade. Frequencies of maximum observed Grade 0-4 toxicity, as defined by the NCI CTCAE v5.0, will be presented for each laboratory parameter. The determination of the maximum grade post-baseline takes into account both planned and unscheduled assessments. Separate summaries indicating hyper- and hypo- directionality of change will be produced, where appropriate.

All laboratory values will be categorized as “low”, “normal”, or “high” relative to the normal ranges, or “unknown” if no valid result is available. For those laboratory parameters that do not have NCI CTCAE v5.0 grading criteria, worst case shift from baseline to post-baseline will be summarized. Shift to low includes normal to low, high to low, and unknown to low. Shift to high includes normal to high, low to high, and unknown to high. If a subject has worst case shifts to both “low” and “high”, the subject will be counted in both categories.

Subjects with elevated worst post-baseline ALT, AST, Total Bilirubin, or alkaline phosphatase (ALP) values that fall into the following categories or other categories as needed will be identified and summarized:

- ALT in the categories of $\leq 1x$ upper limit of normal range (ULN), $>1x$ ULN, $>3x$ ULN, $>5x$ ULN, $>10x$ ULN;
- AST in the categories of $\leq 1x$ ULN, $>1x$ ULN, $>3x$ ULN, $>5x$ ULN, $>10x$ ULN;
- total bilirubin in the categories of $\leq 1x$ ULN, $>1x$ ULN, $>2x$ ULN
- ALP in the categories of $\leq 1x$ ULN, $>1x$ ULN, $>1.5x$ ULN, $>2x$ ULN
- Potential Hy’s law, defined as at least one case of post-dose total bilirubin $> 2 \times$ ULN occurred at the same day or after the first incidence date of ALT or AST $> 3 \times$ ULN post treatment.

For subjects who meet potential Hy’s law criterion, their liver enzyme (ALT, AST, ALP, and total bilirubin) value over time will be plotted.

All laboratory results will be presented by subject in data listings.

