3.5 Definition of Dose-Limiting Toxicity

Protocol-defined DLT criteria are applicable to the dose escalation portion of the study. The determinant period for DLT is the first cycle of treatment (i.e., 28 days for PLD cohorts, 21 days for MIRV cohorts); however, there is provision in the criteria below for AEs that occur beyond this period to be considered in the determination of the RP2D. All toxicities except for CRS and ocular AEs will be graded as per NCI CTCAE v5. CRS will be graded per the American Society for Transplantation and Cellular Therapy (ASTCT) Consensus Grading Criteria for CRS (described in Section 3.7.1.2); ocular AEs for the MIRV cohort will be graded per the tables provided in the Appendix Section 16.6. AEs clearly related to the underlying disease, disease progression, intercurrent illness, or concomitant medications are not considered DLTs. AEs that are clearly related to PLD or MIRV only do not have to be considered DLTs, unless the investigator considers the AE to be exacerbated by SL-172154. DLT is defined as an event considered related or possibly related to SL-172154 and meets one of the following criteria:

- Any death not clearly related to underlying disease or intercurrent illness
- Elevations in liver transaminases (aspartate aminotransferase [AST], alanine aminotransferase [ALT]) or total bilirubin:
 - In subject who enroll with AST/ALT/total bilirubin \leq upper limit of normal (ULN), AST or ALT elevation of $> 8x$ ULN **or** total bilirubin $> 5x$ ULN.
 - In subjects who enroll with AST/ALT/total bilirubin $>$ ULN, AST or ALT elevation of $> 8x$ baseline **or** total bilirubin $> 5x$ baseline.
 - Evidence of Hy's Law (AST or ALT $> 3x$ ULN [or baseline*] with concurrent increase in total bilirubin $> 2x$ ULN [*or baseline] without evidence of cholestasis or alternative explanation such as disease progression or viral hepatitis.

**ULN or baseline dependent on value at enrollment as described above.*

- Any AE that requires permanent discontinuation of SL-172154
- Any Grade 3 or greater AE except for those listed below:
 - Grade 3 fatigue lasting ≤ 7 days
 - Grade 3 anemia
 - Grade 3 or 4 neutropenia not associated with fever (temperature $> 38.5^{\circ}\text{C}$) that improves to Grade 2 within 7 days
 - Grade 3 or 4 lymphopenia
 - Grade 3 thrombocytopenia not associated with clinically significant bleeding and does not require medical intervention

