NOTE: Progression should be calculated from the date of the last administered dose of platinum therapy to the date of the radiographic imaging showing progression.

NOTE: Subjects who are platinum refractory during front-line treatment are excluded [primary platinum-refractory disease, defined as disease that did not respond to (CR or PR) or has progressed within \leq 3 months of the last dose of first-line platinum-containing chemotherapy].

8. **[MIRV Cohort]** Subjects must have received at least 1 but no more than 3 prior systemic lines of anticancer therapy.

Lines of therapy are defined in this study as:

- Adjuvant \pm neoadjuvant is considered 1 line of therapy.
- Maintenance therapy (e.g., bevacizumab, PARP inhibitors) will be considered part of the preceding line of therapy (i.e., not counted independently).
- Therapy changed due to toxicity in the absence of progression will be considered part of the same line (i.e., not counted independently).
- Hormonal therapy will be counted as a separate line of therapy unless it was given as maintenance.

9. **[MIRV Cohort]** Willing to provide an archival tumor tissue block or slides or undergo new biopsy using a low-risk, medically routine procedure for IHC confirmation of FR α positivity.

10. **[MIRV Cohort]** Subject's tumor must be positive for FR α expression defined as PS2+ \geq 25% by the Ventana FOLR1 Assay.

11. Eastern Cooperative Oncology Group Performance Status (ECOG PS) of 0 or 1.

12. Measurable disease by RECIST v1.1 using radiologic assessment.

13. Laboratory values must meet the following criteria.

Laboratory parameter	Threshold value
Absolute neutrophil count (ANC)	$\geq 1.5 \times 10^9/L$ without GCSF in prior 10 days or long-acting WBC growth factors in prior 20 days
Platelet count	$\geq 100 \times 10^9/L$ without platelet transfusion in prior 10 days
Hemoglobin (Hgb)	$> 9.0 \text{ g/dL}$ without packed RBC transfusion in the prior 7 days
Creatinine clearance (CrCl)	$\geq 30 \text{ mL/min}$ (using modified Cockcroft-Gault formula; Appendix Section 16.3)
ALT/AST	$\leq 3 \times \text{ULN}$
Total bilirubin	$\leq 1.5 \times \text{ULN}$; subjects with isolated indirect hyperbilirubinemia are permitted if direct bilirubin ratio is $< 35\%$ and total bilirubin is $\leq 3.0 \times \text{ULN}$
Serum albumin [MIRV cohort only]	$\geq 2 \text{ g/dL}$
Left ventricular ejection fraction (LVEF) [PLD Cohort only]	$> 50\%$ by ECHO/MUGA

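### The SAP's potential Hy's law count has no time window and no baseline reference, so it can include unchanged bilirubin and unrelated late rises; a second, windowed and baseline-referenced row would correct this.

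*SAP*

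**What the plan says.** **SAP 8.4 (Clinical Laboratory Evaluation).** Potential Hy's law needs at least one post-dose total bilirubin above 2x ULN that "occurred at the same day or after the first incidence date of ALT or AST" above 3x ULN. For subjects who meet it, "their liver enzyme (ALT, AST, ALP, and total bilirubin) value over time will be plotted". No window, baseline reference, exclusion of other causes or adjudication step is given.

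**SAP 13.1 and 13.2.** The matching output appears to be Table 14.3.5.5, "Post-Baseline Potential Serious Hepatotoxicity", in the All Treated population. It is kept for the abbreviated CSR. The Hy's law plot (Figure 14.3.5.1) is not.

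**Protocol 3.5 (Definition of Dose-Limiting Toxicity).** Evidence of Hy's law is AST or ALT above 3x ULN or baseline "with concurrent increase in total bilirubin" above 2x ULN or baseline, "without evidence of cholestasis or alternative explanation such as disease progression or viral hepatitis". The choice of reference is "ULN or baseline dependent on value at enrollment as described above". No number of days is attached to the timing. On scope: "Protocol-defined DLT criteria are applicable to the dose escalation portion of the study".

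**Protocol 4.1, criterion 13.** ALT and AST may be up to 3x ULN at entry. Bilirubin may be up to 1.5x ULN, but "subjects with isolated indirect hyperbilirubinemia are permitted if direct bilirubin ratio is" below 35% and total bilirubin is no more than 3.0x ULN.

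**The concern.** Hy's law joins two abnormalities because their occurring together suggests serious liver injury. A rule that lets any later bilirubin complete the pair, and ignores where the subject started, can count pairs that have nothing to do with each other.

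Both routes are plausible here. Eligibility deliberately admits subjects whose bilirubin already exceeds the SAP's 2x ULN threshold. The sponsor's rationale for the hepatotoxicity guidance (Protocol 16.9) says that both SL-172154 and MIRV can raise liver enzymes and that the elevations are transient. One transient ALT peak in Cycle 1 leaves a subject open to a flag from any later bilirubin rise, including one caused by progression, which Protocol 3.5 names as an alternative explanation. At stake is the meaning of the count that the study report gives for serious hepatotoxicity.

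**Working it through.** The plan states no figure for this point, so the check applies the rules to cases.

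**Rules compared**
- SAP rule: let d be the first post-dose day with ALT or AST above 3x ULN. Flag if any bilirubin on day d or later exceeds 2x ULN.
- Protocol-style rule: ALT or AST above 3 x R and bilirubin above 2 x R concurrently, where R = max(ULN, baseline) for each analyte. Reading the reference analyte by analyte is an assumption. Concurrent was read as same visit, then within 7 days, then within 14 days, because the protocol gives no window.

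**Thresholds, in multiples of ULN**

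| Baseline | SAP threshold | Baseline-referenced threshold |
|---|---|---|
| Bilirubin 1.0 | 2 | 2 x 1.0 = 2 |
| Bilirubin 1.5 | 2 | 2 x 1.5 = 3 |
| Bilirubin 2.5 | 2 | 2 x 2.5 = 5 |
| Bilirubin 3.0 | 2 | 2 x 3.0 = 6 |
| ALT 2 | 3 | 3 x 2 = 6 |
| ALT 3 | 3 | 3 x 3 = 9 |

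An unchanged bilirubin meets the SAP's bilirubin limb only if baseline is above 2x ULN. Only the indirect-hyperbilirubinemia exception allows that, so the group is baseline above 2x and up to 3x ULN.

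**Illustrative profiles (multiples of ULN)**

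| Profile | SAP | Protocol-style |
|---|---|---|
| Bilirubin 2.5 throughout; ALT from 1 to 3.5 | Flag | No |
| Bilirubin 2.5 throughout; ALT never above 3 | No | No |
| Bilirubin 1.5 throughout; ALT 3.5 | No | No |
| ALT 4 on Day 9, normal by Day 22; bilirubin 2.5 on Day 64 | Flag | No (all readings) |
| Bilirubin 2.5 from Day 8, still 2.5 when ALT reaches 4 on Day 15 | Flag | Yes |
| Bilirubin 2.5 on Days 8 and 9, 1.8 when ALT reaches 4 on Day 15, then lower | No | No (same visit); Yes (7 or 14 days) |

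In the fourth profile the gap is 64 - 9 = 55 days. A 30-day window would leave it out. In the last profile the gap is 15 - 9 = 6 days, and a two-way window would count it.

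**Does the SAP rule lose concurrent cases?** Take 8 joint visits, each analyte high or not, normal baseline, both high at least once: (2^8 - 1)^2 = 65,025 patterns.
- 58,975 have both high at the same visit. The SAP rule flags all of them.
- It flags 64,256 in total, so 64,256 - 58,975 = 5,281 are flagged without any same-visit overlap.
- Bilirubin is high first in 21,590. Of these, 18,565 have same-visit overlap and none is missed.
- It misses 65,025 - 64,256 = 769, all with bilirubin never above 2x ULN on or after the first ALT/AST crossing.

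The patterns are unweighted. They test the logic and do not estimate incidence.

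**Weight of one flag.** SAP 5.2 reports each regimen separately. Planned totals are 12 + 14 = 26 (PLD) and 12 + 64 = 76 (MIRV), so one subject is 1/26 = 3.8% or 1/76 = 1.3%.

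**The case against.** The SAP calls its category potential. A sensitive screen followed by individual review is a legitimate design, and the rule errs on the safe side. The protocol wording is a DLT criterion for dose escalation. Protocol 9.2.4 specifies no Hy's law laboratory analysis, so the SAP has not departed from one. Other outputs would expose a false flag: the liver function shift table (14.3.5.2.2) relates results to baseline grade and is kept for the abbreviated CSR, ALP categories are tabulated, and listings identify baseline values and are all delivered. Baseline referencing also costs sensitivity: from an ALT of 3x ULN at entry it would require more than 9x ULN.

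All of this stands, and it is why the screen should stay. It does not supply a second step. The SAP has no windowed count, no baseline-referenced count and no label that tells the reader what the number means. In an abbreviated report the count survives and the plot does not.

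Three stronger readings are tempting, and the documents do not support them.
- **That the rule misses cases in which bilirubin rises first.** It does so only if bilirubin has fallen to 2x ULN or below by the first ALT/AST crossing and stays there, and only if concurrent means a window of days.
- **That a count differing from the DLT count is an error.** The two serve different purposes. DLTs have their own table and listing, and the MTD (SAP 8.2) uses DLTs in DLT-evaluable subjects.
- **That the gap is truly unlimited.** The rule sets no limit, but scheduled chemistry ends at the post-treatment visit, about 30 days after last dose.

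**Conclusion.** The point holds as a problem of over-flagging and labelling. As written, SAP 8.4 counts unchanged pre-existing indirect hyperbilirubinemia (baseline above 2x and up to 3x ULN) once ALT or AST exceeds 3x ULN, and it counts late bilirubin rises unconnected with a resolved transaminase peak. It loses no same-visit concurrent case when ULN is the reference.

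The number of subjects affected cannot be estimated from the documents. The first group is narrow; the second depends on how often bilirubin rises late, for example at progression. Nothing shows that dose selection would change, since the RP2D rests on the totality of the data. The case for acting is that a more interpretable count comes from data already collected, at almost no cost. The conclusion assumes that Table 14.3.5.5 carries the SAP 8.4 definition, which its title suggests but the SAP does not state.

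**What to change.** In SAP 8.4 and Table 14.3.5.5:

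1. Keep the present rule as one row, labelled as a sensitive ULN-based screen that is distinct from the Protocol 3.5 DLT criterion.
2. Add a row that requires ALT or AST above 3x and total bilirubin above 2x the reference, within a stated window of each other in either order. Thirty days is an example; the sponsor should fix the window before database lock.
3. Define the reference as ULN if that analyte was at or below ULN at baseline (SAP 5.3.2), and otherwise the baseline value.
4. Show ALP at the time of the paired elevations, so that a cholestatic pattern can be seen.

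The cost is SAP wording, one extra row and a little programming, with no new data. The added row is less sensitive for subjects enrolled above ULN, so it should stand beside the screen. Replacing the screen outright would be a trade-off and is not recommended here.
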